3.0 STUDY ENDPOINTS

3.1 Primary Endpoint

The primary endpoint is a comparison of independent clinical outcome, defined as a modified ordinal Rankin Scale (mRS) at 90 days (scores 5 and 6 combined) among patients randomized to GA versus sedation. Primary analysis will be intention to treat (ITT) and adjusted for stratification variables.

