3.2 Secondary Clinical Endpoints

- 1) As treated analysis of primary outcome adjusted for stratification variables
 - a. Patients will be analyzed according to the type of anesthesia received (e.g., a patient randomized to Sedation that crosses-over to GA will be analyzed in the GA group).
- 2) Dichotomized mRS at 90-days (0-2 vs 3-6) adjusted for stratification variables.
- 3) Angiographic reperfusion defined as modified TICI score $\geq 2b$.
- 4) Early clinical improvement measured by difference in 24-36 hour NIHSS scale.
- 5) Proportion of independent functional outcome at 90 days in GA patients treated with inhalational vs. intravenous medications.
- 6) Difference in quality of life at 90-days.

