3.4 Exploratory Analyses

- 1) Ordinal ITT and as-treated analysis of primary outcome comparing three groups (CS, GA IV, GA inhalational) adjusting for stratification variables.
- 2) Multivariable adjusted analysis (including stratification variables) for both primary (mRS 0-2) and ordinal analysis of 90-day mRS outcomes, to include (but not limited to) baseline variables known to be clinically associated with stroke outcomes:
 - a. Age
 - b. NIHSS
 - c. Time from stroke onset-to-EVT groin puncture
 - d. IV-tPA treatment before EVT
 - e. Atrial Fibrillation
- 3) Duration of time during EVT spent below a systolic blood pressure of 140mmHg.
- 4) Total ICU and ventilator days.
- 5) Subgroup analyses to test for heterogeneity in patient benefit and Provider Skill:
 - a. Proximal vs. Distal occlusion location (ICA+M1-MCA vs. others)
 - b. High-volume vs. low-volume centers
- 6) Costs from a health system perspective

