4.2 Enrollment and Randomization

Enrollment in this study is defined as the moment when the randomization process is completed and the subject is assigned to a study arm. After randomization, no crossover is permitted unless either the neurovascular interventionalist or anesthesiologist determines the patient meets criteria as described in section 5.0. Randomization will occur via a secure, password-protected, web-based system. Subjects will be randomized 1:1 to GA or Sedation using permuted blocks and stratified by center, terminal ICA occlusion (yes/no), and time of stroke symptom onset (≤ 6 hours or 6-16 hours). Patients randomized to GA will subsequently be randomly assigned in a 1:1 ratio to either inhalational or IV anesthesia.

Stroke management and endovascular therapy procedures will occur as per local site usual care. Only FDA-approved thrombectomy devices should be used with first line use of stent retriever. Both general anesthesia and Sedation should be delivered and managed by an anesthesiologist.

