9.0 STATISTICAL METHODS

The study will be conducted under a common umbrella protocol developed by UTHealth with the intention of combining data from all satellite centers for analysis. Each participating site will give utmost importance to follow the study protocol to maintain consistency in study execution at all centers. Detailed analysis plan for all pre-specified outcome measures are located in separate statistical analysis plan.

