9.1 Sample Size Justification

A maximum of 260 patients, 130 per arm will be randomized. Assuming a neutral prior probability (centered at OR of 1.0, 95% prior interval: 0.3–3.0) for the intervention effect, the sample size provides 80% power that General Anesthesia improves outcome (lower ordinal mRS) compared to Sedation if the true OR is >1.50 . Monte Carlo simulations were performed using R to estimate the Bayesian power of the study for the primary outcome measure. We assumed a threshold of 80% posterior probability of the OR >1.0 to declare effectiveness. See Appendix II for summary of simulation results.

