9.2 Statistical Analyses

Intent-to-treat analyses will be performed. To summarize the data, descriptive statistics will be used. Demographics, vital signs, laboratory variables, stroke type and duration from onset of symptoms will be summarized for each treatment arm. Vital signs taken during the treatment period will be displayed graphically. In addition to ICH, other medical events will be tabulated by body system and severity.

Primary analyses will focus on comparing GA (combining inhalational and IV anesthesia) to sedation. All analyses will be conducted under a Bayesian paradigm to obtain estimates of odds ratio (OR) for primary outcome (ordinal mRS), relative risk (RR) for binary outcomes, and probability of treatment benefit or harm (quantities that cannot be obtained from frequentist analyses). For the treatment effect, we will use a neutral prior centered at OR of 1.0 with 95% prior interval of 0.3-3.0. This prior assumes a priori equipoise and excludes large treatment effects. Weakly informative priors will be used for all other parameters to exclude large treatment effects.²⁴

Generalized linear mixed models will be used to analyze all outcomes and will include treatment group, terminal ICA occlusion and time from onset of symptoms (stratification variables) as covariates and center (stratification variable) as a random effect to account for center variability. For the primary outcome of ordinal mRS at 3 months (scores 5 and 6 combined), we will use an ordinal logistic model. For binary outcomes we will use log binomial (or logistic in case of non-convergence) models to directly estimate relative risks (or odds ratios) and 95% CIs. The prior for the treatment effect will be a Normal (0, $sd=0.57$) in the log OR/RR scale. The prior for the intercept will be Normal (0, $sd=10$) and Normal (0,1) for other covariates in the model. A half-Normal(0,1) prior will be used for the standard deviation of the center random effect. For non-binary outcomes, we will select the best fitting models and use neutral, weakly informative priors that exclude large treatment effects. We will examine residuals from each model to ensure reasonable adherence to the assumptions of the models.

If, despite randomization with stratification for center, tICA, and time from onset of symptoms, any important differences between intervention groups occur in baseline variables related to outcome, secondary analyses will be performed controlling for these factors.

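### Section 9.2 ties its additional adjusted analyses to an undefined observed baseline imbalance, while the covariate model that runs regardless (3.4 item 2) is exploratory, open-ended and includes a post-randomization time

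*Combined protocol and SAP*

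**What the plan says.** Most covariate adjustment in the plan is fixed in advance. Section 3.1: "Primary analysis will be intention to treat (ITT) and adjusted for stratification variables". The as-treated analysis in 3.2 is adjusted in the same way, and so is the secondary binary endpoint: "Dichotomized mRS at 90-days (0-2 vs 3-6) adjusted for stratification variables". The comparison of sedation with each type of GA at the end of 9.2 also uses the stratification variables.

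Two places go beyond this set.

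- Section 9.2 adds a conditional rule. If, despite stratification by center, terminal ICA occlusion and onset time, "any important differences between intervention groups occur in baseline variables related to outcome, secondary analyses will be performed controlling for these factors".
- Section 3.4 item 2 lists, among the exploratory analyses, a "Multivariable adjusted analysis (including stratification variables) for both primary (mRS 0-2) and ordinal analysis of 90-day mRS outcomes". It has no imbalance condition. Its covariates are "to include (but not limited to) baseline variables known to be clinically associated with stroke outcomes", followed by age, NIHSS, time from onset to groin puncture, IV-tPA before EVT and atrial fibrillation.

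Neither place refers to the other. Section 9.0 adds: "Detailed analysis plan for all pre-specified outcome measures are located in separate statistical analysis plan". That separate plan is not among the documents supplied.

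**The concern.** In a properly randomized trial, a baseline difference between arms is chance. Adjusting for a variable helps because it predicts outcome, and that can be judged before any data are seen. The 9.2 rule does require the variable to be related to outcome, but it adds the requirement that the variable happened to differ. A strongly prognostic variable that is well balanced is therefore left out, and its precision gain is lost. A weaker one that drifted is put in.

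The rule also leaves open how large a difference must be, which variables are examined, whether the relation to outcome is judged from prior knowledge or from trial data, and who decides. Whether this extra analysis exists, and with which covariates, depends on the data.

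The model in 3.4 item 2 could serve instead, but not as written. Its list can be extended at will, and one of its members is not a baseline variable. At stake is the clarity and precision of a supporting estimate, not the primary result.

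**Working it through.** **1. The plan's own figures.** The 9.2 sentence carries no number, so the check is that the calculation framework matches the trial's.

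- Inputs: sedation rates 10/14/11/19/18/28%, OR 1.53 and 10% crossover from sedation to GA (Appendix II); N = 260 (9.1: "A maximum of 260 patients, 130 per arm will be randomized"); prior Normal(0, sd 0.57) on the log OR (9.2); threshold 0.80.
- The GA distribution under proportional odds is 14.5/18.1/12.6/19.1/15.5/20.3%. The sedation arm as randomized is 0.9 × sedation + 0.1 × GA. Averaging the two arms gives Σp̄³ = 0.0328.
- Information = N(1 − Σp̄³)/12 = 260 × 0.9672/12 = 20.96. Prior precision = 1/0.57² = 3.08.
- Success requires an estimated log OR above 0.8416 × √(20.96 + 3.08)/20.96 = 0.197. The expected ITT log OR is ln 1.465 = 0.382.
- Power = Φ((0.382 − 0.197) × √20.96) = 0.80.
- Type I error: information 260 × (1 − 0.0397)/12 = 20.81; critical z = 0.8416 × √(23.89/20.81) = 0.902; 1 − Φ(0.902) = 0.18.

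The plan states 0.80 and 0.18. A 4,000-trial simulation gave 0.796 and 0.186.

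**2. How often the 9.2 rule fires by chance.** Allocation is 1:1 (4.2: "Subjects will be randomized 1:1 to GA or Sedation using permuted blocks"), so 130 per arm. The standardized difference of a covariate then has SD √(2/130) = 0.124. The readings of *important* and the number of candidates k are assumptions, and the covariates are taken as independent. P(fires) = 1 − (1 − q)^k, where q is the chance that one variable qualifies.

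| Reading of *important* | q | k = 5 | k = 10 |
|---|---|---|---|
| p < 0.05 | 0.05 | 23% | 40% |
| p < 0.10 | 0.10 | 41% | 65% |
| standardized difference > 0.2 | 0.107 | 43% | 68% |
| standardized difference > 0.1 | 0.420 | 93% | >99% |

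For five candidates, the number named in 3.4 item 2, the undefined word alone moves the rule from firing in about one trial in four to firing in nearly all.

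**3. What a fixed set gains over a triggered one.** Illustrative simulation, 2,000 trials per setting (Monte Carlo standard error about 1 percentage point). Assumptions not in the documents: five independent standard-normal covariates with log-odds coefficients 0.5, 0.7, 0.2, 0.2 and 0.2 per SD. Center and the stratification variables are omitted. Share of trials with Pr(OR>1) > 0.80:

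| Setting | No covariates | Triggered | Five fixed |
|---|---|---|---|
| OR 1.53, trigger p < 0.05 | 73% | 74% | 79% |
| OR 1.53, trigger difference > 0.1 | 73% | 77% | 80% |
| OR 1.0, trigger p < 0.05 | 18% | 18% | 19% |
| OR 1.0, trigger difference > 0.1 | 20% | 18% | 19% |

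A second check, with assumed R² of 0.3 and an effect of 0.21 SD, gave 79% unadjusted, 81% triggered and 86% fixed. Both runs show the same order: the trigger keeps only part of the precision that a fixed set gives, and neither approach raises the null rate materially.

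**4. The 3.4 item 2 list against the time of randomization.** The synopsis sets randomization as study time 0, and anesthesia during EVT is what is assigned. Age, NIHSS at baseline, thrombolysis already given and atrial fibrillation precede it. Groin puncture is the start of EVT (5.1 item 4) and comes after assignment. Section 1.2 says GA may bring more delay to recanalization, and 7.4 allows up to 5 minutes for arterial access attempts before GA induction. Onset-to-puncture time can therefore depend on the arm, and adjusting for it could remove part of the effect being estimated. Pre-randomization onset time is already a stratification variable (≤6 or 6-16 hours, 4.2).

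**The case against.** The strongest reply is that the plan already has what is asked for. Section 3.4 item 2 runs whatever the balance, with five named covariates, so a covariate-adjusted OR exists in every realization of the trial. The primary and the listed adjusted mRS secondary analyses use a fixed set. All of this stands. It confines the point to the single 9.2 sentence and to the status and contents of the 3.4 list. It does not cure either of them.

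Three stronger readings are tempting, and the documents do not support them.

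- *A triggered analysis could reverse the trial's success verdict.* Success rests on the primary posterior probability (synopsis; 9.1). No section lets a secondary analysis declare or overturn it.
- *The trigger inflates false positives or creates disagreement near 0.80.* In the simulations above, the triggered analysis alone crosses under the null in about 18% of trials, no more than the unadjusted model. Disagreement with an unadjusted model follows from any adjustment: at an assumed R² of 0.3 it is about 12.6% for an always-run covariate model against 5.6-6.8% for a triggered one. Such figures therefore do not argue against the trigger.
- *Covariates are chosen after seeing unblinded outcomes.* The plan does not say who decides or when. Comparing arms needs arm-level baseline data, not outcomes.

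The separate analysis plan cited in 9.0 may define the criterion or the candidates. If it does, the protocol text should be aligned with it.

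**Conclusion.** The point holds as a minor weakness in pre-specification. The 9.2 sentence ties an additional analysis to chance imbalance through an undefined criterion. The model in 3.4 item 2 that could replace it is exploratory, open-ended and includes a variable measured after assignment.

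The primary analysis, the 0.80 success rule and N = 260 are untouched. The benefit of a change is freedom from data-driven covariate choice and better precision in one secondary analysis. In the first illustrative simulation a fixed set reaches the bar about 3 to 5 percentage points more often than triggered adjustment, and 5 points more often (86% against 81%) in the second. These gains depend on the assumed covariate strengths. They are also not a gain over the whole plan, because 3.4 item 2 already gives a fixed model in exploratory status. The 23-93% range depends on the assumed thresholds, five candidates and independence. The case against onset-to-puncture time rests on the plan's own sequence and needs no simulation.

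**What to change.** 1. In 9.2, delete the sentence that makes adjusted analyses conditional on baseline differences. In its place, name the 3.4 item 2 model as the one adjusted secondary (sensitivity) analysis of 90-day mRS, run regardless of observed balance with the 9.2 models and priors.
2. In 3.4 item 2, remove the words that leave the list open, drop onset-to-groin-puncture time, and close the list before unblinding: age, baseline NIHSS, thrombolysis given before randomization, atrial fibrillation and the stratification variables. Wording this as thrombolysis rather than IV-tPA also covers tenecteplase, which 5.1 admits.
3. In the same item, correct the label that calls mRS 0-2 primary. The primary endpoint in 3.1 is ordinal.
4. State that any adjustment for an unexpected imbalance is reported as post hoc.

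The cost is a few sentences in two sections, with no change to data collection or sample size. The one thing given up is ad hoc adjustment with secondary-analysis status.

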9.3 Missing Data

If patients are lost to follow-up at the 90-day end of study evaluation, the worst-case scenario will be entered into the database (i.e., mRS = 6). In the event that the percent of patients lost to follow-up exceeds 5%, we will use multiple imputation methods. This technique quantifies the uncertainty due to the missing data.

9.4 Safety Monitoring

Formal interim analyses of safety will occur when 100 and 200 patients are enrolled. Safety endpoints will consist of intracerebral hemorrhage within 18-36 hours and death. Bayesian interim monitoring will be used to assess whether systematic differences are evident among the treatment groups for the occurrence of the interim safety analysis endpoint. The posterior probability that either treatment group has a higher incidence of the interim safety analysis endpoint will be determined. These posterior probabilities for safety will be assessed using the log-binomial regression model with covariates, described more completely in section 9.2. Either treatment will be considered harmful (i.e., the DSMB may consider termination of the trial) if the posterior probability of treatment harm in one treatment arm compared to the other exceeds 97.5%. In addition to reporting the above posterior probability, the 95% credible interval for the RR, and the entire posterior distribution of RR will be presented graphically to the DSMB in order to assure a full appreciation of the range of possible values of each RR.

9.5 Interim Efficacy Analysis

One interim analysis is planned after the first n=132 patients (50% of data accrual) have been randomized and have completed the 3-month primary outcome assessment. Ordinal mRS outcome will be compared between GA and CS groups using a Bayesian logistic model detailed in section 9.2. The same neutral priors will be used to calculate posterior probabilities of benefit for either treatment group. Posterior median OR and 95% intervals will also be calculated.

During the interim analyses of efficacy, the DSMB may consider termination if the posterior probability of benefit (improving independent clinical outcome) of either treatment arm compared to the other is greater than 95%. Given that this is a comparative effectiveness trial, no interim futility analyses will be conducted since they are not appropriate for evaluating therapies already in use.²⁷

10.0 DATA MANAGEMENT

10.1 Data Collection

Detailed clinical data collection will be performed using an established standard method approved by each site's IRB. Data will be de-identified and recorded initially on paper CRFs and then transferred to the study's secure web-based application.

Every reasonable effort should be made to complete data entry within one week of data collection. Data discrepancies may be queried during ongoing review of data by the trial's data coordinating center (DCC) or may be identified and queried during remote or in-person monitoring visits. Data monitoring will be performed to verify data accuracy and ensure queries are resolved. The Principal Investigator or Sub-investigator must ensure the accuracy and completeness of the recorded data and then provide his/her electronic signature on the appropriate CRFs.

Each participating center will provide appropriate source documentation for data monitoring. Data monitoring can take place either remotely (review of eCRFs compared with uploaded, deidentified s

designee of the trial PI. Remote data monitoring will require the site to scan the appropriate source documents. After scanning, local sites will be required to redact all patient identifiers. Finally, the redacted file will be saved and uploaded to the trial website's secure repository. The DCC will be responsible for comparing the eCRF data and the uploaded source documents.

11.0 STUDY COMMITTEES AND CORE LABS

11.1 Steering Committee

The steering committee will be responsible for oversight of the overall conduct of the study. These duties include protocol development and amendments, study progress, and overall data quality and integrity. The Steering Committee will oversee dissemination of study results through appropriate scientific meetings and publications. The Steering Committee may select additional investigators, based on enrollment, to participate on a Publication Committee. The Publication Committee will participate in the review and approval of all requests for data analysis, abstract and manuscript preparation and journal submission.

11.2 Data Safety Monitoring Committee

The Data Safety Monitoring Committee (DSMB) will include specialists in stroke neurology, neuro-intervention and biostatistics, none of whom are participating in the trial or have affiliation with the trial sponsor, UTHealth. The DSMB is responsible for monitoring subject safety through pre-defined, periodic review of the clinical study safety data. Details regarding DSMB responsibilities, qualifications, membership, meeting frequencies, and procedures are outlined in the DSMB charter.

The trial's un-blinded biostatistician will assist the data-core in preparing blinded DSMB reports. Data will be supplied to, and reviewed by, the DSMB as tables and/or figures. The DSMB can request more data. At each review the DSMB will evaluate whether the study should continue unchanged, require modification/amendment or be closed to enrollment and will inform the trial Co-PIs.

The principal investigator (study sponsor), DSMB or the Institutional Review Board (IRB) have the authority to terminate, suspend, or require trial modifications.

11.3 Imaging Core Labs

An independent imaging core lab will blindly review baseline parenchymal and vascular imaging that is performed as each site's routine care of acute ischemic stroke patients who may be eligible for EVT. The image-core interpretations of all neuroimaging will serve as the data source for analyses such as ASPECTS score, hemorrhage and hemorrhage classification (see table 5) and angiographic measures of occlusion, reperfusion and collateral grade (see table 4). Baseline imaging will usually include a non-contrast CT of the head, CT-angiogram of the head +/- neck and to a lesser degree, a CT-perfusion of the head. According to local practice, baseline MRI and MRA are also accepted.

Follow-up neuroimaging (CT or MRI) that is routinely collected between 18-36 hours post thrombolysis or EVT will be used to determine the presence of infarction and hemorrhage. Conventional cerebral angiograms will be assessed for pre-intervention (e.g., diagnostic [first intracranial run] angiogram) clot location and TICI score. Reperfusion, graded using the modified TICI reperfusion score, will be recorded by the imaging core lab post EVT. Additional angiographic scales will be assessed including but not limited to collateral flow grade. All neuroimaging will be de-identified at the local site

and submitted to the sponsor DCC either digitally in DICOM format via a secure FTP portal or saved to a CD-ROM disc and mailed directly to the DCC.

Table 5. Definition and description of intracranial hemorrhage.

Intracranial Hemorrhage	Definition
HT-1	Hemorrhagic Transformation Type 1. Small, scattered petechiae within ischemic field without mass effect.
HT-2	Hemorrhagic Transformation Type 2. Confluent petechiae within ischemic field without mass effect
PH-1	Hematoma within ischemic field with some mild space-occupying effect but involving $\leq 30\%$ of the infarcted area
PH-2	Hematoma within ischemic field with space-occupying effect involving $> 30\%$ of the infarcted area
RIH	Any intraparenchymal hemorrhage remote from the ischemic field
rPH-2	PH-2 remote from the ischemic field
IVH	Intraventricular hemorrhage
SDH	Subdural Hematoma. Blood between the dura mater and the arachnoid mater
EDH	Epidural Hematoma - Blood between the dura mater and the skull
SAH	Subarachnoid hemorrhage

